The Veterans managed by the VA Healthcare System are complex, often with chronic conditions and multiple physical and mental health comorbidities. In particular, diabetes results in many complications and negative outcomes, leads to high medical costs¹, requires intense self-management, and is complicated by changing recommendations for care. Over 20% of VA patients struggle with Type 2 diabetes², and effective management is even more complicated for those with co-morbid mental health conditions or living in rural areas. Rural Veterans with diabetes are more likely to have a higher number of comorbidities and to have both medical and mental health comorbidities³.

Virtual care technologies have the potential to improve diabetes outcomes⁴⁻⁹ and research shows that diabetes self-management plans are more likely to work when they are designed to fit patients' priorities, resources, and lifestyles, and are supported by virtual care technology.¹⁰ Patient portals have been described as secure online websites that offer patients convenient access to personal health information and are connected to a healthcare organization with features that support tasks like communicating with providers, requesting prescription refills, reviewing test results and managing appointments. Although there is insufficient evidence that patient portal use improves overall health outcomes,¹¹ web- and portal-based interventions have shown quite promising results for diabetes management^{5,12-16}.

My HealthVet (MHV) is the VA's personal health record portal. Registration with MHV enables Veterans to create a password-protected account to record and track personal goals and manage medications by refilling VA prescriptions (Rx Refill). Veterans who also complete an in-person authentication process receive Premium accounts linked with their CPRS records which enables access to the full array of portal features, including the ability to Secure Message (SM) with VA clinical team members, view VA chemistry/hematology results, view upcoming VA appointments, receive tailored wellness reminders (7 of the 12 are directly relevant to diabetes care), and access extracts from their CPRS records, including VA progress notes and VA medication history through the Blue Button (BB) "Download My Data" feature.

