During the COVID-19-related suspension of in-person interactions with research participants, in-person group trainings and one-on-one trainings cannot take place. Those patients who have already been invited to attend an in-person training and expressed interest in attending will be invited to attend a virtual training instead through VA Video Connect (VVC) or a similar virtual modality such as Zoom. They will also be informed that an in-person training *may* be offered in the future. The virtual group and one-on-one trainings will follow the same format as the in-

person trainings. The VA trainer will share screens showing YouTube videos, Powerpoint slides, guidance documents and the My HealtheVet test account. The trainer will provide virtual guidance as the participants practice logging into and exploring their own My HealtheVet accounts.

Unless the administrative hold on in-person interactions with human research subjects lifted at the time when invitation letters are mailed to participants randomized to Encouragement Arm 3 for the one-on-one trainings, we will mail the amended letter inviting participants to an online training instead.

In this protocol, whenever “group trainings” or “in-person trainings” are mentioned, during the COVID-19-related suspension of in-person interactions with research participants starting 3/18/2020, these trainings refer to virtual trainings.

If the COVID-19-related suspension of in-person interactions with research participants is lifted before the study is completed, then in-person group trainings and one-on-one trainings may be offered again to the invited patients. If it no longer fits into the timeline of the study to offer the trainings, they will not be offered.

All Veterans will be invited to participate in the phone interview, regardless of which arm they are in, or whether they participated in in-person trainings that might have been offered to them. At the end of the Aim 3 intervention, all Comparison arm study participants who did not opt out or did not have an undeliverable mail address will be mailed a training guide.

5. Study Subject Selection

Sample Description

All participants will be Veterans aged 18 and older.

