This aim builds on prior study aims and involves the refinement and pilot testing of an intervention. Using a randomized encouragement design, we will randomize 200-300 Veterans ages 18-85 years old from the Bedford/Boston VAMCs with uncontrolled diabetes ($HbA1c > 8.5$) and no or minimal prior history of using the key MHV features to receive an invitation to one of the following groups, after they have been mailed a brochure and have had the opportunity to opt out of the study. We will aim for each encouragement arm to have at least 50 Veterans, and for the comparison arm to have 50+ enrolled Veterans.

- 1) Comparison arm: My HealtheVet brochure only
- 2) Encouragement arm 1: My HealtheVet brochure and training guide
- 3) Encouragement arm 2: My HealtheVet brochure and training guide plus offering a group training

- 4) Encouragement arm 3: My HealtheVet brochure and training guide plus offering a group training and a one-on-one session

We estimate that 15 to 25 (30-50 percent) of those randomized to each of the 3 encouragement arms will choose to participate by using the training guide or attending a group training or one-on-one session. Feedback on the intervention and patients' intent to use MHV will be gathered from the patient at the one-on-one meeting, the group session, and during their phone interview.

a. Subject Inclusion Criteria

Our primary inclusion criteria are that Veterans:

- Are current VA Bedford or VA Boston patients (including CBOC patients)
- Have uncontrolled diabetes ($HbA1C \geq 8.5$ at last test)
- Are inactive users (registered but with at least 1 year of non-use) or non-users of My HealtheVet
- Have an upcoming health visit scheduled at Bedford VA or Boston VA.
- Are age 18-85 years old at approximate time of first mailing

b. Subject Exclusion Criteria

Veterans are excluded if they do not meet the above criteria (e.g., they are already active MHV users, their most recent HbA1c at the time of recruitment was $< 8.5\%$, or they are age 86 and over at the time of the initial mailing).

c. Recruitment

Subject Identification and Pre-Enrollment Screening:

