Data analysis requires the use of information regarding enrolled patients' usage of My HealthVet for both recruitment and analysis, which would be biased if consent were required. We already have access to data describing their use of My HealthVet via a previous study Aim, therefore we are requesting a waiver of documentation of consent. We will provide all participants with an information sheet (modified consent form) containing information about their rights and any risks of participation, as well as study team contact information, with the initial mailing so that they will have time to review it prior to deciding whether or not to opt-out of the study.

6. Data Collection/ Study Measures

Data Collection:

For each in-person component of the intervention (group trainings and one-on-one sessions), Veterans will be asked to complete an immediate post-intervention feedback evaluation measuring their intent to use features of My HealthVet covered in the trainings. We will follow all Veterans randomized to the encouragement arms and comparison for 4-6 months and measure the number of My HealthVet features used, and the frequency with which they use them. We will look at My HealthVet use data of everyone invited to participate in the study.

Beyond this quantitative data, we will also conduct a semi-structured phone interview and demographic questions with Veterans in all arms at 4-6 months, seeking feedback on the intervention components and on their continued intent to use MHV for communication and

information sharing with VA and non-VA providers. The interview will be expected to last 15-20 minutes. We will not audiotape interviews. The interviewer will take notes on paper and/or enter responses into a secure VA REDCap database.

Feasibility data on the resources and time expended for intervention delivery will also be gathered to inform future implementation. All project staff will document hours spent planning training sessions, running training sessions, and interacting with participants over the phone. We will also document costs expended on printed materials and any other incurred project expenses.

7. Planned Statistical Analyses

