Analysis Plan. For this small-scale experiment, we will focus our primary analyses on measuring the effect of the randomized encouragement design on the key proximal process measure of using MHV. We will measure MHV use, including the variety of features (SM, Rx Refills, EHR-extracts (Blue Button, lab views), and frequency of feature use. Because we are interested in the effect of the intervention in the sample targeted, we will conduct an intent-to-treat analysis based on randomization arm regardless of participation in intervention components. As many in the encouragement arm will not participate, this ITT does not directly assess the intervention-attributable effect. Thus, in addition to ITT, we will utilize a complier average causal effect (CACE) analysis to estimate intervention effects for those who engaged with the intervention. CACE estimation makes it possible to estimate the intervention effect for only those who engage. The CACE estimation considers both random assignment and receipt of treatment to estimate intervention efficacy. CACE estimations have been published using instrumental variables, expectation-maximization algorithm, maximum-likelihood, and integrated methods. CACE seeks to compare outcomes for individuals in the intervention condition with those who would have complied with treatment given the opportunity to do so and can often be used to improve power over ITT methods. Like all instrumental-variable methods, CACE estimation requires that certain assumptions be met: that randomization has a causal effect on the exposure (relevance assumption), that the randomization affects the outcome only through the exposure (exclusion restriction), and that randomization and the outcome (MHV use) don't share a common cause (exchangeability assumption). If these assumptions are violated or the instrument is weak, we will fall back on an ITT analysis, using the chi-square test as the statistical test to determine the effect of receiving encouragement on MHV use.

Power: Below, we provide power for ITT analyses, and anticipate additional power when implementing the CACE. We will have power to detect reasonable differences in use of MHV. We have used pilot data, looking at Veterans who did not use the patient portal in 2013 and

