The primary benefit for participants will be that they may learn how to use My HealthVet in order to support their own health. Patients that are randomized to the encouragement arm will receive a training guide and support to help them learn how to use My HealthVet. In addition to the guide, depending on their arm, they may receive assistance with signing up for an authenticated account with My HealthVet, participate in (and, if desired, have caregivers participate in) a one-on-one session, or group training on how to use the My HealthVet portal. Additionally, project staff will be available to answer questions regarding the My HealthVet portal. In sum, participants will receive knowledge regarding the My HealthVet portal and its uses as well as information on ways to interact and communicate with their medical care providers via MHV.

Alternative Procedures:

Not applicable

c. Analysis of Risks in Relation to Benefits

All staff is trained in HIPAA compliance and will complete all human subjects training. Training of staff will include information about the importance of confidentiality and techniques to maintain confidentiality of all information reported by research participants. Individual identifier information will be removed from study data files and transcripts, as soon as possible. Unique study-specific identifiers will be assigned to support accurate linkage of data on the same individuals across multiple data files (including surveys, in-depth interview recordings and transcripts, etc.). The participant code will appear on data forms, including surveys, and abstracted audio taped forms/recordings. A file stored separately from the data will contain participant identifiers and codes. Data, recordings, and transcripts will be destroyed when feasible and in accordance with VHA Records Control Schedule. In no way will individual participant data be released to the public or cited in a publication.

Aim 2 Interviews will be audio-taped using a VA approved digital recorder and audio-recordings will be stored on a VA secure server with limited access. Transcription will be completed by an internal VA transcription service or local staff. Electronic data, including any paper forms scanned into electronic form will be stored on a VA secure server with limited access. All paper records will be stored in locked file cabinets in locked offices, with access limited to those with appropriate training and IRB approval.

d. Stopping Rules

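### Most counted portal features need an in-person-authenticated account, but the analysis ignores baseline account status, so a null on number or variety of features could mean lack of access rather than failed training

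*Combined protocol and SAP*

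**What the plan says.** Section 2 (Background Information) describes two levels of account. Registration alone lets a Veteran track goals and refill prescriptions. Beyond that, "Veterans who also complete an in-person authentication process receive Premium accounts linked with their CPRS records", and this Premium account opens secure messaging, laboratory results and Blue Button extracts.

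Section 7 (Analysis Plan) defines the outcome as use of the portal, including "the variety of features (SM, Rx Refills, EHR-extracts (Blue Button, lab views), and frequency of feature use". The hypothesis in Section 3 concerns the number and variety of features used. Section 6 sets the observation window: "We will follow all Veterans randomized to the encouragement arms and comparison for 4-6 months".

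The eligibility criterion in Sections 4 and 5a reads: "Are inactive users (registered but with at least 1 year of non-use) or non-users of My HealtheVet". Account level is not mentioned. Randomisation is blocked by site only, and Section 7 names no account-related stratum, covariate or subgroup.

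Section 4 describes the guide, the group session and the one-on-one session without mentioning authentication. For virtual delivery, Section 4 (2020 Coronavirus modifications) says: "The trainer will provide virtual guidance as the participants practice logging into and exploring their own My HealtheVet accounts". The only reference to authentication help is in Section 8b, which says of encouragement-arm patients that, beyond the guide, "depending on their arm, they may receive assistance with signing up for an authenticated account with My HealthVet".

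**The concern.** A participant with no Premium account can take up everything offered and still be unable to score on most of the outcome. If few extra features are used in an encouragement arm, there are two explanations with opposite lessons: the training did not change behaviour, or it did and the account stood in the way. A feasibility trial is run largely to tell such explanations apart, and the plan as written cannot.

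The complier average causal effect analysis does not separate them either. Someone who studies the guide or attends a session but is not authenticated counts as engaged with no use of Premium features, which lowers the complier estimate in the same way.

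The second cost is statistical. Whether someone already has an account is likely to predict whether they use the portal within 4 to 6 months, and the unadjusted test discards that information.

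**Working it through.** **1. Features by account level** (Section 2 set against Section 7)

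| Feature counted in Section 7 | Account needed according to Section 2 |
|---|---|
| Prescription refill | Registration |
| Secure messaging | Premium |
| Blue Button extracts | Premium |
| Lab views | Premium |

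Three of the four need Premium. A basic account caps the variety score at 1 of 4.

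**2. Where authentication is delivered**

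- Guide (Section 4): logging in, password reset, basic tips and feature sections. Authentication is not named.
- Group and one-on-one sessions (Section 4): how to access and use core features, including Blue Button and secure messaging. Authentication is not named.
- Virtual sessions (Section 4): practice in the participant's own account. As Section 2 describes it, a video call cannot itself be the in-person step.
- Section 8b: help is possible and depends on arm. Neither the arms nor the mode is given.

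These passages are not carried through to one another.

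**3. The plan's own sample-size figure**

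Inputs from Section 7 (Power): comparison use 1% + 1% = 2%; encouragement use 0.30 × 0.50 = 15%; alpha 0.05, taken as two-sided; power 80%.

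n per arm = [1.960 √(2 p̄(1 − p̄)) + 0.842 √(p₁(1 − p₁) + p₂(1 − p₂))]² / (p₂ − p₁)²

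With p̄ = 0.085: [1.960 × 0.394 + 0.842 × 0.384]² / 0.13² = 1.20 / 0.0169, about 71 to 72 per arm. Power at 70 per arm is 79.4%. The stated 70 per arm reproduces. It is powered on any use, which prescription refill alone can satisfy.

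**4. How sparse the data will be**

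At 70 per arm: 70 × 0.02 = 1.4 comparison users and 70 × 0.15 = 10.5 encouragement users. At the planned minimum of 50: 1.0 and 7.5. This limits the number of strata.

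**5. Whether a two-stratum test is safe and useful**

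The documents give no rates by account status, so this simulation rests on assumptions: registered share 25%, 50% or 75%; use among the registered 1, 3, 6 or 10 times that among non-users in both arms; overall rates held at 2% and 15%; 50 or 70 per arm. Compared with the plain chi-square test, the two-stratum Mantel-Haenszel test changed power by between about −1 and +6 percentage points. The small losses came where status predicted little or where most participants were registered; the largest gains came where a minority was registered and used the portal far more. Its type I error did not exceed 5%. The statistical gain is modest, and the main benefit is interpretation.

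**The case against.** The strongest reply is that access may not be blocked at all. Section 8b foresees authentication help. The guide is written for new users but is not reproduced in the documents, so a summary's silence does not show that authentication is missing from it. Registered inactive users may already hold Premium accounts. Every participant must have an upcoming VA visit, where authentication might be possible, and the suspension described in Section 4 covers in-person research contact, not the VA's own account process. Interviews in all arms could bring access problems to light. All of this stands. A reader might infer that the guide-only arm and the virtual sessions fail to give access; the documents show only that delivery is not described.

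A reader might also infer a large loss of power. If 25%, 50% or 75% of would-be users were blocked, cutting 15% in proportion while leaving the comparison arm at 2% would give 60%, 33% or 9% power at 70 per arm. That calculation is not supported. The blocked shares have no source. The 2% and 15% are any-use rates, which refills can satisfy without a Premium account. The same barrier applies in the comparison arm, and scaling both arms gives 66%, 48% and 26% instead. The 50% uptake forecast may already allow for account barriers. No power figure of this kind should be used.

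Finally, removing an account barrier is a legitimate way for a supported-adoption intervention to work, so arm differences in that help are part of what is being compared. That is right for the intent-to-treat effect. It does not help anyone explain a null.

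**Conclusion.** The concern holds as one of interpretation and unused information. Three of the four named features depend on an account level that the plan neither measures at baseline nor uses in the analysis, and the sections describing delivery are not reconciled with the one that mentions authentication help.

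A reader might infer that the main comparison is biased. It is not: randomisation balances account status in expectation, and the intent-to-treat effect remains valid for the population targeted.

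The size of any attenuation cannot be computed, because the documents give neither the share without a Premium account nor rates of use by status. The conclusion rests on Section 2's description of the account levels. The remedy assumes that screening data separate registered inactive users from non-users, as the eligibility criterion implies. It is a low-cost improvement to the analysis, not a flaw that undermines the trial.

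**What to change.** In Section 7:

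- Stratify the intent-to-treat test by baseline registered/non-user status (for example Mantel-Haenszel with two strata), or adjust for it as a covariate. Use no more than two strata; crossing status with site would give four, too many for 1 to 2 expected comparison users per 70.
- Report results descriptively by that status, and by Premium status if the portal data contain it. The documents do not say that they do.
- Report the Premium-only features separately from prescription refill.

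Settle this wording before use data are examined by arm.

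In Sections 4 and 8b: state which arms receive authentication help and how this works under virtual delivery, so that the two sections agree.

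The analysis changes need only text and, on the assumption above, data from screening. The downside is sparse strata, so subgroup results should carry no formal claims. A new prompt to authenticate, added to mailings or calls, is not recommended: some patients had already been invited when the March 2020 changes were written, so earlier and later participants would receive different encouragement.

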If the potential participant does not wish to participate, they can contact study staff by telephone at the number listed on the letter introducing the study. They can also mail the opt-out postcard in order to be removed from contact lists. Potential participants who do NOT indicate that they wish to opt out of future communication from the team within approximately 10 business days of the mailing will be assumed to be enrolled in the study, unless we hear from them to opt-out at a later time. If participants opt out after randomization, we will no longer contact them for other portions of the study. However, we will look at data that we already have for these participants from Aim 1. Those receiving the information sheet (modified consent form) will be informed of the general nature of the study, what their involvement entails, the risk/benefits, and a description of confidentiality. Participants will be told that participation is voluntary, that they can withdraw at any time, and that this will not impact their treatment.

Consistent with the adaptability of a randomized encouragement design, those that do not opt-out will be divided randomly into 4 arms, with at least 50 Veterans in the encouragement arms and at least 50 participants in the comparison arm. Bedford and Boston participants will have separate randomization blocks.

- 1) Comparison arm: My HealthVet brochure only
- 2) Encouragement arm 1: My HealthVet brochure and training guide
- 3) Encouragement arm 2: My HealthVet brochure and training guide plus offering a group training
- 4) Encouragement arm 3: My HealthVet brochure and training guide plus offering a group training and a one-on-one session

All participants in encouragement arms 1-3 will be mailed a paper copy of a training guide. This guide was developed as part of this study based on findings from Aims 1 and 2 and Veteran co-investigator input and does not exist anywhere else. It cannot be posted on a publicly accessible website as this would threaten randomization.

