Patients will be considered enrolled in this portion of the study if they do not opt out of the study. If participants opt out after randomization (by returning the opt-out postcard or leaving a voicemail message for the project staff), we will no longer contact them for other portions of the study. Not participating in an in-person training or a telephone interview will not be considered opting out. However, even if patients opt out, we will still look at data that we already have for these participants from previous study aims. Those receiving the information sheet (modified consent form) will be informed of the general nature of the study, what their involvement entails, the risk/benefits, and a description of confidentiality. Participants will be told that participation is voluntary, that they can withdraw at any time, and that this will not impact their treatment.

HIPAA Authorization:

This is a minimal risk study and we are requesting a waiver for the study.

We will protect identifiers, as outlined in this protocol (see **Data Security**) and destroy the identifiers in accordance with the VA records control schedule. PHI will not be used and or disclosed to any other person or entity, except as required by law, for authorized oversight of the

research study, or for other research for which the use of disclosure of the requested information would be permitted by the Privacy Rule.

Because study materials will be distributed via mail, we are requesting a HIPAA authorization waiver. Additionally, a HIPAA authorization waiver is necessary because requiring participants to complete and return a HIPAA waiver may bias our study results (i.e., those who return the waiver may have different clinical profiles or experiences on My HealthVet (i.e., be more active) than those who might not return the form).

We will protect identifiers, as outlined in this protocol (see modified consent form or information sheet) and destroy the identifiers in accordance with the VA records control schedule. PHI will not be used and or disclosed to any other person or entity, except as required by law, for authorized oversight of the research study, or for other research for which the use of disclosure of the requested information would be permitted by the Privacy Rule.

Informed Consent:

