Because there is a small risk that participants may experience some distress or psychological discomfort when answering survey or interview questions, participants will be made aware of their right to refuse to answer any questions that make them uncomfortable or that they do not wish to answer, and they will be informed of their right to withdraw from the study at any time without penalty. Participants may also be informed that they can take breaks. Additionally, study staff will be trained to respond to emotional distress and to discuss concerns and issues should they arise. If a participant becomes very distressed during the phone conversation, we may directly transfer the Veteran to the Veteran Crisis Hotline. This will be conducted via a “warm handoff.” Prior to study staff contacting the “Veteran Crisis Hotline (VCH),” study staff will request the participant’s contact number and/or take note of the telephone number via the caller ID (if available). Study staff will try to maintain contact with the participant until he/she is connected to the VCH. Participation in this research project is voluntary. Refusal to participate in the research project will involve no penalty or loss of rights to which veterans are entitled. If they choose to participate, they may withdraw from this study at any time without penalty or loss of VA or other benefits to which they are entitled. If they withdraw from the study, the data provided may be used in our analysis, unless otherwise requested.

If they decide they do not wish to participate in any part of the study, they can simply return the enclosed Opt-Out Card immediately or call us, and they will not be contacted again.

9. Safety Monitoring Plan

a. Data Security

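### Does opting out after randomisation remove a Veteran from the intent-to-treat analysis?

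*Combined protocol and SAP*

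**What the plan says.** Section 4 (Study Design) says that a participant who opts out after randomisation is no longer contacted, and continues: "However, we will look at data that we already have for these participants from Aim 1". Section 5c (Recruitment, Enrollment) repeats the rule in slightly wider terms: "we will still look at data that we already have for these participants from previous study aims". It also limits what counts as opting out: "Not participating in an in-person training or a telephone interview will not be considered opting out".

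Section 6 (Data Collection/Study Measures) sets the outcome follow-up: "We will follow all Veterans randomized to the encouragement arms and comparison for 4-6 months". It adds: "We will look at My HealthVet use data of everyone invited to participate in the study".

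Section 7 (Analysis Plan) specifies an "intent-to-treat analysis based on randomization arm regardless of participation in intervention components".

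Section 8d (Stopping Rules) has a general withdrawal clause: "If they withdraw from the study, the data provided may be used in our analysis, unless otherwise requested".

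**The concern.** The outcome arises after randomisation. The two opt-out passages name only data already held from earlier aims, and the word *already* suggests records that predate the opt-out. On that reading, someone who opts out during follow-up has no outcome and leaves the intent-to-treat set. Section 7 does not rule this out, because its wording concerns people who skip intervention components, and Section 5c says that skipping a training or interview is not opting out.

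Contact after randomisation differs by arm, so opt-out could differ too. Section 4 states: "All participants in encouragement arms 1-3 will be mailed a paper copy of a training guide". Arms 2 and 3 also receive training invitations and scheduling calls. During follow-up the comparison arm gets only the interview invitation that every arm gets. If opt-outs were excluded and used the portal at a different rate from the rest of their arm, the comparison of arms would be biased. If their use was the same, the cost would be some power.

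**Working it through.** **Step 1: can the passages all be followed together?**

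- *Sections 4 and 5c.* These contain one prohibition (no further contact) and one permission (earlier-aim data may be used). Neither forbids extracting later administrative records.
- *What opting out means.* Sections 4 and 8d describe it in terms of communication: the person leaves the contact lists and hears no more from the team.
- *Section 6.* This section governs outcome collection. It follows all randomised Veterans and examines use data for all who were invited, a group that includes opt-outs.
- *Source of the outcome.* Portal use is recorded passively, so ending contact does not end measurement. Under Informed Consent in Section 5c the team says that it already has access to portal-use data through an earlier aim. The earlier-aim data are therefore of the same kind as the outcome. Their dates are not given in this Aim 3-only document, so the text does not show that they stop before follow-up.
- *Section 7.* Analysis is by randomised arm.

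These statements are compatible if opting out ends contact only. The intent-to-treat set is then everyone randomised.

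**Step 2: the plan's own figure (Section 7, Power).**

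Comparison-arm use is 100% − 98% = 2%. Encouragement-arm use is 0.30 × 0.50 = 15%. The difference is 13.0 points. The usual two-proportion formula (two-sided 0.05, 80% power, no continuity correction) gives 72 per arm, and 70 per arm gives 79.4% power. The plan's 70 per arm for 80% is reproduced.

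**Step 3: what if opt-outs were excluded after all?**

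The plan gives no opt-out rate, so the rates here are assumptions. With true use p, opt-out rate o and use u among opt-outs, the observed rate is (p − o·u)/(1 − o).

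| Opt-out, encouragement vs comparison | u = p | u = p/2 | u = 0 |
|---|---|---|---|
| 5% vs 1% | 13.0 | 0.14625/0.95 − 0.0199/0.99 = 13.4 | 0.15/0.95 − 0.02/0.99 = 13.8 |
| 10% vs 2% | 13.0 | 0.1425/0.90 − 0.0198/0.98 = 13.8 | 0.15/0.90 − 0.02/0.98 = 14.6 |
| 20% vs 2% | 13.0 | 0.135/0.80 − 0.0198/0.98 = 14.9 | 0.15/0.80 − 0.02/0.98 = 16.7 |

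(Results are differences in percentage points.)

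- *No bias from unequal opt-out alone.* The first column stays at 13.0 although the opt-out rates differ by arm. Bias needs opt-outs whose use differs from the rest of their arm.
- *Either direction is possible.* If opt-outs used the portal at twice their arm's rate (u = 2p), 20% vs 2% opt-out would give (0.15 − 0.20 × 0.30)/0.80 − (0.02 − 0.02 × 0.04)/0.98 = 0.1125 − 0.0196 = 9.3 points, a shift of −3.7.
- *Scale.* The standard error at 70 per arm is √(0.15 × 0.85/70 + 0.02 × 0.98/70) = 4.6 points. The largest shift shown is 3.7.
- *With no true effect.* If use is 2% in both arms, opt-out is 20% vs 2% and no opt-out uses the portal, the spurious difference is 0.02/0.80 − 0.02/0.98 = 0.5 points.
- *Power if opt-out is unrelated to use.* The exact power of the uncorrected chi-square test is 85% at 70 vs 70. At 10% vs 2% opt-out (63 vs 69 analysed) it is 83%, and at 20% vs 2% (56 vs 69) it is 79%. The 85% and the 79.4% in Step 2 describe the same design; the gap is exact calculation against normal approximation.

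**The case for a change.** The strongest case for a change is that no sentence expressly places the follow-up data of post-randomisation opt-outs in the intent-to-treat analysis. Several phrases lean the other way. Sections 4 and 5c make enrolment conditional on not opting out, and the consent-waiver rationale speaks of the portal use of enrolled patients. The commitment to examine everyone invited also covers people who opted out before randomisation and have no arm, so it cannot by itself define the analysis set. The withdrawal clause in Section 8d speaks of data provided, and it is unclear whether that includes passively recorded portal use. Two data managers might therefore extract different sets, and settling the matter once opt-outs by arm are known would be a post hoc choice. A clarifying sentence would cost little.

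The absence of an express sentence stands, and so does the point about Section 8d. The rest carries less weight. The analysis set is fixed by randomisation, not by continuing enrolment, and the Section 6 commitment to follow all who were randomised matches that set exactly. The commitment on everyone invited is wider still, and it does not fit a policy of discarding opt-outs. A clarifying sentence would write down what Section 6 already commits to and would leave the planned analysis as it is. The group affected is also narrow: people have about 10 business days to opt out before randomisation, and non-attendance afterwards does not count.

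**Conclusion.** The plan needs no change on this point. The opt-out passages leave a detail unstated, and Sections 6 and 7 lead an analyst to fill it sensibly: contact stops, administrative use data continue, and the Veteran is analysed in the assigned arm. A person who asks that their data not be used falls under the exception in Section 8d.

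This rests on reading opt-out as an end to contact, which the text supports but does not spell out. The coverage of the Aim 1 data and the participant information sheet cannot be seen here. If opt-outs were excluded instead, bias would arise only where their portal use differed from the rest of their arm, and it could go either way. In the scenarios examined (assumed opt-out up to 20% vs 2%, use among opt-outs from none to twice their arm's rate), the shift is at most 3.7 points against a standard error of 4.6. That range illustrates the size and is not a bound, because the plan gives no opt-out rate.
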